Study Design	Phase 1 open label single arm dietary
	intervention study
Study Center	The Ohio State University

Primary Objective	Renal MRI (non-contrast) measures of total
	kidney volume to assess disease progression,
	cyst growth/progression, and stiffness/fibrosis
Secondary Objective	Urine microalbumin, eGFR, body mass and
	composition
Number of Subjects	20 patients

Inclusion Criteria	1. Age 18-65 years old
	2. Diagnosis of ADPKD by imaging
	and/or genetic testing
	3. GFR $\geq$ 25 mg/dl
	4. Patients at risk for rapid progression
	of ADPKD: Mayo Class 1C-1E along
	with any other high risk features
	including early decline in GFR,
	hypertension onset $\leq$ 35 years of age,
	urologic events $\leq 35$ years of age,
	PKD 1 truncating mutation and
	PROPKD score of 4 or higher as
	determined by the treating physician
	5. No changes of medications within the
	last three months.
	6. Able to comply with dietary
	intervention
	7. Ability to sign informed consent
Exclusion Criteria	1. Patients currently being treated with
	Tolvaptan
	2. Diagnosed with diabetes.
	3. Pregnancy
	4. Contraindications to MRI
	5. Ketogenic diet within the last three
	months
	6. Severe kidney disease with GFR < 25
	mg/dl
	7. Unable to purchase food for the diet
	intervention
	8. Gastrointestinal disorders that will
	interfere with diet intervention
	9. Chronic alcohol or drug abuse

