# RESEARCH STRATEGY

This is a prospective study to determine ketogenic diet effect on htTKV, GFR, microalbuminuria. This is a single-center study of 20 patients with ADPKD and deemed high risk for progression to ESRD. This determined by combination of features of ADPKD and htTKV as assessed by prior computed tomography (CT) or MRI. Patients will be recruited from the Polycystic Kidney Disease (PKD) Clinic at Ohio State University Wexner Medical Center. Enrolled patients will have MRI for htTKV, urinary studies, blood tests at baseline, 6 months, and 52 weeks. Blood for GFR will be assessed three times over the course of the study including baseline, 6 months, and 1 year. Participants will follow ketogenic diet for 52 weeks. The [name] Lab Nutrition Team will manage the ketogenic diet.

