#### DATA ANALYSIS AND STATISTICAL METHODS

The study will focus on percent change for TKV, albuminuria, and GFR pre and post the ketogenic dietary intervention. We will collect the following data for each patient including age, sex, race, baseline medications, BMI, albuminuria, GFR, and blood pressure. The univariate analysis will include the above variables and use analysis of variance to assess changes at baseline and at 12 months. Based on the univariate analysis, we will perform linear regression. Ketogenic diet administration will be forced into the model. Other variables will be chosen based on strength of the univariate analysis. Our outcome of interest will be percent change in TKV, albuminuria, and GFR. In regard to MR Imagining, we will utilize a statistical method to account for observer variability. Statistical techniques such as intra-class correlation coefficients (ICC) can quantify the level of agreement between different observers and help correct for any bias.

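### The univariate step screens regression covariates by their own change over time, not by their relation to the outcome, and its analysis of variance is not stated to be paired

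*Protocol*

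**What the plan says.** The Study Synopsis describes the design as "Phase 1 open label single arm dietary" intervention study, and Research Strategy adds: "This is a single-center study of 20 patients with ADPKD and deemed high risk for progression to ESRD". There is no control group, so every comparison is between two times in the same people.

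Data Analysis and Statistical Methods first puts the outcomes on a within-patient scale: "The study will focus on percent change for TKV, albuminuria, and GFR pre and post the ketogenic dietary intervention". It then lists the variables to be collected: "age, sex, race, baseline medications, BMI, albuminuria, GFR, and blood pressure". TKV is not on that list. The next sentence is the one at issue: "The univariate analysis will include the above variables and use analysis of variance to assess changes at baseline and at 12 months".

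A linear regression follows, with the diet forced in as a term. The rule for the remaining terms is: "Other variables will be chosen based on strength of the univariate analysis". The section restates the outcome: "Our outcome of interest will be percent change in TKV, albuminuria, and GFR".

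The protocol does not say whether the analysis of variance is paired, repeated-measures, one-way or independent-groups. It gives no SD, correlation, significance level, power or interval width.

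**The concern.** Two things are run together in one sentence: estimating how measures change over the year, and finding which patient characteristics go with a better or worse course.

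As worded, the step asks whether each listed variable differs between baseline and month 12. For sex and race the question has no content. For age the answer is the same year for everyone. Baseline medications have no month-12 value by definition, although medications are recorded at later visits. For BMI and blood pressure the question is sensible, but its answer is then used for something it cannot inform, namely which covariates belong in a model of percent change. The rule would favour whatever the diet moves most and would leave out fixed characteristics that may matter.

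The second issue is the error term. Values from one patient at two times are correlated. An analysis of variance that ignores this puts between-patient spread into the error and makes true changes look uncertain. GFR is on the list and is also used to monitor progression (Monitoring Plan, Timing of Monitoring). A real fall reported as not significant could be read as reassurance about the diet.

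**Working it through.** **No figure to reproduce.** The plan states no numerical precision or power for this step. From the protocol: n = 20, one arm, measurements at baseline and 12 months. All correlations and SDs below are assumptions, shown as ranges.

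**A. The screening rule.** For a listed variable X, let d = X at month 12 minus X at baseline, and let Y be the patient's percent change in the outcome.

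- Repeated-measures form: F = [mean(d) / (SD(d)/√20)]², the squared paired t.
- Independent-groups form: F = mean(d)² / (pooled variance × 2/20).
- What covariate choice needs: the association of baseline X with Y.

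Unless X is itself the outcome, neither F contains Y. Shuffling the Y values among the 20 patients leaves both F values unchanged but alters the association with Y completely. Applied literally:

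| Variable | Change, baseline to month 12 | Result of the step |
|---|---|---|
| Sex, race | 0 in every patient | no test of change exists (0/0 in the paired form) |
| Age | the same year in every patient | nothing to learn |
| Baseline medications | no month-12 value | cannot be computed |
| BMI, blood pressure | can change | shows whether they moved, not whether they predict Y |
| GFR, albuminuria | can change | these are outcomes, so this tests the outcome and does not screen predictors |

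**B. The width penalty, if raw values are analysed as independent groups.** With cross-sectional SD σ, equal at both times, and correlation r:

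- Unpaired 95% half-width = t(0.975, 38) × σ√(2/20) = 2.024 × 0.3162σ = 0.640σ, whatever r is.
- Paired 95% half-width = t(0.975, 19) × σ√(2(1−r)/20) = 2.093 × σ√((1−r)/10).
- Ratio = (2.024/2.093)/√(1−r) = 0.967/√(1−r).

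| Assumed r | Paired half-width | Unpaired / paired |
|---|---|---|
| 0.3 | 0.554σ | 1.16 |
| 0.5 | 0.468σ | 1.37 |
| 0.7 | 0.363σ | 1.77 |
| 0.8 | 0.296σ | 2.16 |
| 0.9 | 0.209σ | 3.06 |
| 0.95 | 0.148σ | 4.33 |
| 0.99 | 0.066σ | 9.67 |

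The ratio reaches 2 only at r of about 0.77, and 3 at about 0.90.

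For GFR with an assumed σ of 25 ml/min, the unpaired half-width is 0.640 × 25 = 16.0. The paired half-width is 0.468 × 25 = 11.7 at r = 0.5, 0.296 × 25 = 7.4 at 0.8, 0.209 × 25 = 5.2 at 0.9 and 0.148 × 25 = 3.7 at 0.95.

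**C. Error rates under the same condition** (40,000 simulated trials per r, n = 20, nominal 5%). For a shift that the paired test detects with 80% power, the unpaired test has about 54% power at r = 0.5, 10% at 0.8 and 0.8% at 0.9. Its type I error falls to 0.7% at r = 0.5 and below 0.1% at 0.8. The error is therefore one of missed changes, not false positives.

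**D. When there is no penalty.** In a simulated data set with two times, the repeated-measures F and the squared paired t were both 0.0192. A percent change is one value per patient, so analysing it also keeps the pairing.

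**The case against.** A reader might infer that the plan treats 20 baseline and 20 month-12 values as 40 independent observations, with intervals several times too wide. The protocol does not say so. Analysis of variance includes the repeated-measures form, which at two times is the paired t test. Which form is fitted is the kind of detail a statistical analysis plan may settle. The declared outcomes are percent changes, which are within-patient already, and TKV, the primary measure, is not on the list that the step is applied to. The size of any penalty rests on a correlation that the protocol does not give, and at r of 0.3 to 0.7 it is only 1.2 to 1.8 times. All of this stands.

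The percent-change wording does not settle the matter, though. One percent change per patient cannot be compared between baseline and month 12, so the disputed sentence seems to concern raw values. The forced diet term points the same way: everyone receives the diet, so with one row per patient that term is a constant. It varies only if baseline rows (off diet) and month-12 rows (on diet) are stacked, which is the layout where pairing is easily lost. This is an inference that keeps the unpaired reading open; it does not establish it.

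It can also be said that, since the step feeds a regression, it was meant as analysis of variance of percent change across levels of sex, race and so on. That would be ordinary and meaningful, and it means one cannot claim that sex and race could never be selected. But the sentence describes change between two times, so if that was the intent it needs rewriting.

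**Conclusion.** The concern holds in two parts of different strength.

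1. Taken as written, the covariate screen uses the wrong criterion and is applied partly to variables that cannot meaningfully change. This does not depend on the form of analysis of variance or on any assumed number. It depends only on reading the sentence literally.

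2. The missing paired form is an ambiguity with a conditional cost. If independent groups are used on raw values, intervals are too wide by roughly 1/√(1−r): about 1.4 times at r = 0.5, 2.2 at 0.8, 3.1 at 0.9 and 4.3 at 0.95. With repeated measures or percent change the cost is nil.

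Severity is moderate. This is a 20-patient, uncontrolled Phase 1 study with no stated test level or power, and the conditional error is conservative. Still, missing a real fall in GFR would be an unhelpful direction in which to err.

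**What to change.** Replace the univariate sentence and the selection rule with text to this effect:

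- Changes from baseline to 12 months in TKV, GFR, albuminuria, BMI and blood pressure are estimated within patient, by a paired t interval or a repeated-measures or mixed model, with 95% confidence intervals.
- TKV, albuminuria and GFR stay on the declared percent-change scale. A log ratio back-transformed to percent change is acceptable, provided the text says so.
- Age, sex, race and baseline medications serve only as baseline descriptors or as predictors of change, and are not tested for change.
- Any predictor is judged by the association of its baseline value with the patient's own percent change in the outcome.

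The cost is a few sentences in the protocol or the statistical analysis plan. No new data, visits or patients are needed. It is best settled before the 12-month data are seen.

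### Regression covariates are to be picked by univariate strength from eight candidates, so p-values and intervals for the covariates that are picked will be misleading

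*Protocol*

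**What the plan says.** All of the relevant method is in one paragraph of the Protocol, Data Analysis and Statistical Methods.

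- Candidates: "We will collect the following data for each patient including age, sex, race, baseline medications, BMI, albuminuria, GFR, and blood pressure".
- Screen: "The univariate analysis will include the above variables and use analysis of variance to assess changes at baseline and at 12 months".
- Model: "Based on the univariate analysis, we will perform linear regression".
- Forced term: "Ketogenic diet administration will be forced into the model".
- Selection: "Other variables will be chosen based on strength of the univariate analysis".

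The outcomes are percent change in kidney volume, albuminuria and GFR, so the procedure may be run three times. The paragraph gives no entry threshold, no limit on the number of covariates and no correction for selection, and it does not call the model exploratory.

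The Study Synopsis describes the design as "Phase 1 open label single arm dietary", and Research Strategy gives the size: "This is a single-center study of 20 patients with ADPKD".

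**The concern.** Screening candidates one at a time against the outcome and then fitting the winners in an ordinary regression uses the same data twice. A variable enters because its observed association is large, and the final model then tests that association as though it had been chosen beforehand. Its p-value is too small and its interval is centred too far from zero.

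The design offers little in return. Every patient receives the diet, so there is no treatment contrast to adjust for confounding. What the selected model mainly adds is statements about which patients changed more, and those are the statements whose error rates fail. A later study could take such a false predictor as a lead.

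**Working it through.** **Inputs from the protocol.** Eight candidates (counted from the quoted list), 20 patients, one arm, three outcomes. The protocol gives no figure for this step, so there is none to reproduce.

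**Assumptions.** Entry threshold *a* = 0.05, 0.10 or 0.20; final tests two-sided at 5% with 95% intervals; no candidate truly related to the outcome; the screen tests association with the outcome. Candidates are normal, either independent or with pairwise correlation 0.5.

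**Step 1: chance of retaining at least one noise variable.** For independent candidates this is 1 − (1 − a)^8:

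- a = 0.05: 1 − 0.95^8 = 33.7%
- a = 0.10: 1 − 0.90^8 = 57.0%
- a = 0.20: 1 − 0.80^8 = 83.2%

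Simulation at n = 20 (6,000 null trials per setting) agrees: 32.5%, 57.4% and 82.9%. The expected number retained is 8a = 0.4, 0.8 and 1.6. With correlation 0.5 the simulated retention falls to 25.5%, 44.1% and 70.6%.

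**Step 2: what the final model says about a retained noise variable.** A null p-value is uniform, so given that it passed the screen, the chance that it is below 0.05 is 0.05/a = 100%, 50% and 25%. Fitting several retained variables together lowers this slightly. Because the true coefficient is zero, coverage is one minus the rejection rate. Simulated at n = 20:

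| Entry threshold | Rejected at nominal 5%, independent | Coverage of nominal 95% interval | Rejected, correlation 0.5 |
|---|---|---|---|
| p<0.05 | 87% | 13% | 49% |
| p<0.10 | 44% | 56% | 17% |
| p<0.20 | 22% | 78% | 8% |

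Repeat simulations with independent candidates gave 84-89%, 42-44% and 22-23%. If the single strongest variable is always kept instead, its nominal 5% test rejects in 33% of null trials.

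**Step 3: is the small sample the cause?** The formula in step 1 contains no n. Simulated retention at n = 200 is 32%, 56% and 82%, essentially the same.

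**Step 4: is screening the cause of false significant covariates overall?** With screening, 27-31% of null trials at n = 20 end with at least one significant covariate. Fitting all eight with no screening already gives about 26%. Most of that rate is therefore multiplicity. What screening itself damages is the error rate of the covariates reported, which is step 2.

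**Step 5: the mean change.** With covariates centred, the intercept is the mean percent change. Its nominal 5% test rejects in 5.8% to 7.4% of null trials after screening. If covariates are not centred, the intercept is the predicted change at a covariate value of zero and should not be read as the mean change.

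**The case against.** The strongest objections, and what remains of each:

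- **An unseen statistical analysis plan may supply the detail.** It may supply a threshold, a cap and an exploratory label, and their absence alone would not be a finding. But the protocol itself fixes selection by observed strength. No threshold makes nominal p-values valid after that, so the point stands.
- **The candidates are not all noise.** This is fair. The protocol's Summary and Background names early hypertension and GFR decline as signs of rapid progression, so blood pressure and GFR may be truly prognostic. Baseline GFR and albuminuria are also the denominators of two of the three percent-change outcomes. The all-noise case is a benchmark, not a forecast. A reader might infer that the selected variables will mainly be chance findings; the protocol does not support that. What remains is that the rule cannot tell real from chance associations.
- **The screen is ambiguous.** Read literally, the analysis of variance tests change between baseline and 12 months, not association with the outcome. That reading makes little sense for sex or race, but the text is unclear, and the figures above apply to the association reading only.
- **Correlated candidates soften the effect.** They do. At correlation 0.5 and p<0.20 the rejection rate of 8% is not far from nominal. At p<0.05 it is still 49%.
- **No objective concerns predictors.** This is correct: the stated objectives are about kidney volume, GFR and albuminuria, and the paragraph does not promise covariate p-values. The harm arises if the selected coefficients are reported and interpreted, which is the usual purpose of such a model.

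**Conclusion.** The point holds for covariate coefficients. The protocol states a selection rule that, under the assumptions above, retains at least one of eight noise candidates in about 33%, 57% or 83% of trials when they are independent and about 26%, 44% or 71% at correlation 0.5. With independent candidates, the nominal 95% interval for a retained noise covariate covers only about 13% to 78% of the time. The thresholds, the correlation and the absence of real effects are assumptions, not protocol figures.

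Two stronger readings are not supported. A reader might infer that 20 patients are too few for the rule and that a larger sample would cure it. Retention depends on the number of candidates and the threshold, and it is the same at 200; the small sample is a reason for few covariates, not the source of these figures. A reader might also infer that the main pre-post result is undermined. It is only mildly affected, at about 6-7% against 5%.

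This is a correction worth making, but it does not put the study's main estimate in doubt. The same paragraph has a separate, more basic problem: a diet term that is constant across all patients cannot be estimated apart from the intercept.

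**What to change.** Delete the sentence that selects covariates by univariate strength. State that the main analysis of each outcome is the within-patient change from baseline to 12 months with its 95% confidence interval.

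If a regression is kept, name at most one or two covariates in advance from baseline data already collected, centre them, select none by p-value, and label the model exploratory. Each coefficient then has its nominal error rate under the usual linear-model assumptions. The chance of any false significant covariate per outcome falls to about 1 − 0.95² = 9.75% with two covariates (about 9% in simulation).

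The change is to wording only, with no added patients, visits or measurements, and should be made before outcome data are analysed. The downside is that fewer exploratory associations will be reported.

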#### **OUTCOMES**

**Study Endpoints:** Change in total kidney volume (TKV) from baseline to 1 year to assess disease progression. Change in albuminuria and GFR.

**Primary Objective:** The primary Objective will be to determine htTKV at baseline and 1 year after ketogenic diet intervention.

**Secondary Objectives:** The secondary endpoints will be measurement of GFR and 24-h urine microalbumin.

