# **Study Procedures:**

Serological Assessment and Health monitoring

Visit 1(Baseline):

- Record patient's medical history, including extrarenal manifestations
- Medications
- Pregnancy history if applicable
- Vitals
- Physical Exam
- Patients will undergo MRI non-contrast for evaluation of htTKV
- Blood will be drawn for baseline assessment of GFR, urine osmolality, and urine microalbumin to creatinine ratio
- Blood samples will be saved for metabolomics analysis
- Body composition will be assessed by dual-energy x-ray absorptiometry (DXA)
- Finger Stick BHB: Finger sticks will be taken daily in the morning, by the participant to determine ketone and glucose levels in a fasted state. Measurements will be reported daily in RedCap or Qualtrics.

CGM/CKM: Continuous Glucose Monitoring (CGM) and Continuous Ketone Monitoring (CKM) will be performed. This involves applying a sensor patch on the back of the arm to measure metabolites in interstitial fluid. The sensor can capture data for 2-weeks.

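### Untransformed percent change in albuminuria, analysed by mean-based methods with no control arm, is biased upward and loses power to show a fall, substantially if within-patient variation is large

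*Protocol*

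**What the plan says.** The outcome scale is stated twice under Data Analysis and Statistical Methods: "The study will focus on percent change for TKV, albuminuria, and GFR pre and post the ketogenic dietary intervention", and again "Our outcome of interest will be percent change in TKV, albuminuria, and GFR". The same section says the univariate step will "use analysis of variance to assess changes at baseline and at 12 months", and then "Based on the univariate analysis, we will perform linear regression". Both methods work on means. No log transform, geometric mean, median or rank method appears anywhere in the protocol.

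Albuminuria is a secondary endpoint. Under Outcomes: "The secondary endpoints will be measurement of GFR and 24-h urine microalbumin". The Study Synopsis describes the design as "Phase 1 open label single arm dietary" intervention, and Research Strategy adds "This is a single-center study of 20 patients with ADPKD".

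The urine measure is described in two ways. Outcomes names a 24-hour collection, while the Visit 1 and Visit 6 lists under Study Procedures give a "urine microalbumin to creatinine ratio".

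**The concern.** A halving of albuminuria scores -50% and a doubling scores +100%. One patient of each kind averages +25%, although the two changes are equal and opposite on a ratio scale. A few patients with large rises can therefore dominate the mean.

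In a randomised comparison a similar shift would arise in both arms and would partly cancel. Here there is one arm, so the shift goes straight into the before-and-after estimate. With 20 patients the sample is too small for the t approximation to absorb strong skewness.

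The error runs against the study's own hypothesis. A real reduction may be missed, or a rise may be reported in patients on the diet when the typical patient has not changed.

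**Working it through.** **Inputs from the protocol.** n = 20; single arm; baseline and 12 months; outcome is percent change; mean-based analysis. There is no SD, effect size, alpha or power for albuminuria, so there is no figure of the plan's own to reproduce.

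**Assumptions.** The log of (12-month / baseline) albuminuria is normal with SD s, and s is varied from 0.2 to 0.9. The test is two-sided at 5%. A one-sample t test on percent change stands in for the stated mean-based analysis, and is compared with the same test on the log ratio. Error rates and power come from simulation (40,000 to 100,000 trials per setting).

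**Step 1. Expected mean when nothing changes.** E[percent change] = 100 × (exp(s²/2) − 1). For s = 0.5 this is 100 × (exp(0.125) − 1) = +13%. It is positive for every s above zero.

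**Step 2. False findings when nothing changes, n = 20 (nominal 2.5% in each direction).**

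| s | Expected mean | False rise | False fall |
|---|---|---|---|
| 0.2 | +2% | 4.5% | 1.4% |
| 0.4 | +8% | about 7% | 0.8% |
| 0.5 | +13% | about 9% | 0.6% |
| 0.7 | +28% | about 13% | about 0.3% |
| 0.9 | +50% | about 16% | 0.2% |

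On the log ratio, each direction stays at about 2.5%.

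**Step 3. Power to show a true 30% fall in the geometric mean, n = 20.**

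| s | Percent change | Log ratio | Share of log-ratio power lost |
|---|---|---|---|
| 0.3 | 99% | 100% | about 1% |
| 0.4 | 85% | 97% | 12/97 = 12% |
| 0.5 | 59% | 86% | 27/86 = 31% |
| 0.6 | 36% | 71% | 35/71 = 49% |
| 0.7 | 21% | 58% | 37/58 = 64% |
| 0.9 | 8% | 39% | 31/39 = 79% |

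**Step 4. When does the expected sign reverse under a true 30% fall?** E[percent change] = 100 × (0.7 × exp(s²/2) − 1). This gives −21% at s = 0.5, −11% at s = 0.7 and +5% at s = 0.9. It crosses zero at s = √(2 × ln(1/0.7)) = 0.84.

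**Step 5. Sensitivity to dropout.** With 16 patients the results are similar. At s = 0.5, for example, power for a 30% fall is 52% on percent change against 76% on the log ratio.

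**The case against.** **A transform may be left to the analysis plan.** The protocol does not use the words arithmetic or mean, and it does not exclude a transform. A statistical analysis plan, not shown here, could specify one, and a back-transformed log ratio is also a percent change. The sentence on analysis of variance could even be read as comparing values at the two visits. This has some force. However, the protocol names percent change twice and pairs it with two mean-based methods, so an untransformed mean is the natural reading. The outcome scale is thus stated, not merely left open.

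**Bias is relative to a target.** The mean percent change is biased only against the geometric mean (or median) change, and the protocol does not say which summary it wants. That is correct. The error rates above are false positives in the sense that the typical patient has not changed.

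**Stronger readings.** A reader might infer that most of the power to see a fall is lost. The documents do not support that without a condition. They give no SD; for a 30% fall almost nothing is lost at s of 0.3 or below, about a third at 0.5, and half or more only from about 0.6. A reader might also infer that the result would be reported with the wrong sign. The expected sign under a 30% fall reverses only above s of about 0.84.

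**Limited consequence.** This is a secondary endpoint in a small Phase 1 study with no stated power. The log ratio itself reaches only 58% and 39% power at the two largest SDs, and no change of scale allows a single-arm result to be attributed to the diet. All of that stands, and it limits the weight of the point.

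**Conclusion.** The point holds in conditional form. As written, the albuminuria analysis is biased upward relative to the typical change at every SD examined, with lopsided error rates: a false rise in about 4.5% to 16% of trials for s from 0.2 to 0.9, against 2.5%. Power for a fall is reduced, slightly when within-patient variation is low and substantially when it is high.

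The direction follows from log-normal variation alone. The size rests on the assumed s and on a t test standing in for the stated methods. The point concerns albuminuria only; it is not a claim about kidney volume or GFR. It is worth correcting because the alternative is better at almost no cost, but it does not threaten the primary objective.

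The mismatch between a 24-hour measure and a creatinine ratio is a separate contradiction and lends no support to the skewness argument.

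**What to change.** For albuminuria, replace percent change as the analysed quantity with log(12-month / baseline) within patient. Report the geometric mean ratio with its 95% CI, back-transformed to a percent change so that readers still see the familiar scale. Any regression for this endpoint should use the same log ratio.

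Separately, reconcile the Outcomes section with the Study Procedures lists so that one urine measure, 24-hour microalbumin or the microalbumin to creatinine ratio, is named as the endpoint and used at both times.

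The analysis change costs one sentence of wording and needs no new data or visits. Naming the measure is also an edit to the text; if the 24-hour measure is kept, the visit lists must show that collection.
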